There are 3 distinct projects within this follow-up study, the aims and objectives have been divided by project to clearly demonstrate how they will be implemented:

Project 1:

The aim of project 1 is to refine our estimates of diagnostic accuracy of MR imaging as a technology to aid the prenatal diagnosis of fetal developmental brain abnormalities.

- 1) We will reassess the diagnostic accuracy of MR imaging compared to antenatal US through:
 - a) Measurement of diagnostic accuracy of antenatal US alone (i.e. prior to iuMR) relative to updated reference diagnosis at 2-3 years of age (post-natal imaging or post-mortem examination);
 - b) Measurement of diagnostic accuracy of iuMR (following antenatal US) relative to the updated reference diagnosis at 2-3 years of age (post-natal imaging or post-mortem examination).

Project 2:

The aim of project 2 is to improve the prognostic information available during pregnancy based on the functional and developmental outcomes of the MERIDIAN cohort.

- 1) We will quantify the value of prognoses based on MR imaging and on USS by:
 - a) Assessing the concordance between severe neurodevelopmental impairment (defined by BSID score of <80 on the Cognitive AND language index or a combined score of <85 or a motor score of <70, evidence of severe disability based on a score <-2SDs for the ASQ, or evidence of cerebral palsy based on GMFCS) and poor prognosis, based on MR and on USS;
 - b) Comparing the relative prognostic accuracy of USS and MR imaging;
- 2) We will qualitatively assess the cases for which the USS prognosis and MR prognosis differed, in relation specifically to the original diagnoses;
- 3) We will look at the concordance in the subgroup of children for which the MR scan was performed within 24 weeks;
- 4) We will assess ability to predict non-severe impairment (defined as BSID <85 or a score between 1 and 2 SDs for the ASQ).

Project 3:

The aim of project 3 is to assess the clinical significance of isolated, mild ventriculomegaly.

- 1) We will assess the clinical significance through:
 - a) Identification of all isolated, mild ventriculomegaly cases diagnosed on in utero MR in the MERIDIAN cohort and define their developmental outcome at 2-3 years (as per project 2);
 - b) Comparison of developmental outcome to the prognoses made based on USS.

3. Study design

Multi-centre observational cohort study of diagnostic accuracy and functional development of children born from the MERIDIAN study.

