The Ages and Stages Questionnaire (ASQ) [15] will also be posted out or given to participants to complete and return with the consent form. If participation is declined at this stage then this will be recorded on the Approach form using the original MERIDIAN participant ID number and no further contact will be made. If the ASQ is returned but the consent form is not, then we will assume consent for using the information provided on the ASQ.

If the consent form or ASQ are not returned after 3 weeks of posting to them the research team will send a reminder letter and a second copy of the forms or a reminder text message can where appropriate.

Project 2

Involvement in project 2 will also be discussed during the telephone or face to face contact to determine interest. If participants indicate during this contact that they would like to participate in project 2 as well as project 1 then the combined consent form will be posted out/completed face to face.

Once the appropriate consent forms have been returned the research team will arrange a suitable time and place for the assessment to be completed.

To optimise follow up, if a face to face meeting cannot be arranged, or an appointment is missed there will be the option for data collection via parent completed questionnaires. These questionnaires can be posted out or completed over the telephone.

It will be made clear to the participant that participation in project 2 is entirely optional and does not affect their involvement in project 1.

Consent for Project 1 only will be captured on consent form project 1. Consent for Project 1 and 2 will be captured on the combined consent form.

6. Assessments and procedures

Project 1 (case note review)

Once the completed consent form has been returned to the research team they will review the child's medical notes and record details of further follow up, additional or changed diagnoses, postnatal imaging and other investigations relating to the child's development.

Where, during screening, it is identified that the child is no longer alive then date of death and cause of death will be collected and recorded. In some instances this information may be available from the HSCIC. Where this data is not available from the HSCIC a review of medical notes and hospital records will need to be completed to collect this data.

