If the family do not consent, if no further scans or investigations have been undertaken, or the child died during the initial MERIDIAN then the original reference diagnosis used in MERIDIAN will be retained.

The research team will complete the CRF with details from the case note review. The Ages and Stages questionnaire will also have been posted to participants along with the consent form. The results of this questionnaire will be calculated and recorded.

In most cases, the case note review CRF will be completed at the MERIDIAN research site. If the child is no longer alive the central research team may be required to populate this form with the date of death and cause of death as provided by the HSCIC or equivalent, where appropriate approvals are in place.

For any contentious cases our independent expert panel (consisting of a fetal medicine clinician, paediatric neuroradiologist and paediatric neurologist or neurosurgeon) will adjudicate whether additional diagnoses are likely to be acquired conditions (i.e. those which are not detectable by fetal imaging and does not relate to conditions which are, such as infant meningitis); or a congenital pathology that would have been detected by optimal fetal imaging.

If the participant consented to Project 1 only the research team at site will post the Parent Debrief Letter once the case note review has been completed.

Project 2 (Detailed neurodevelopmental assessment)

The assessments will be completed face to face in a hospital, local clinic or, in the participant's home.

The Bayley Scales of Infant Development (BSID) [14] will be used to assess developmental outcome. It is a well validated tool for assessing development in early infancy that is widely used and generates standardised scores that allow corrections for differences in age at measurement. The BSID is an assessment of global infant development, however in a small minority of children with very complex impairments (e.g. spina bifida where children are in a wheelchair) a BSID will not be possible, but we will still complete the Gross Motor Function Classification System (GMFCS) [16] or the adapted Gross Motor Skills questionnaire and Strengths and Difficulties Questionnaire (SDQ) [17], as detailed below.

The GMFCS and the SDQ will also be administered during this appointment. Details of the additional assessments are provided in appendix 1.

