- b. Measurement of diagnostic accuracy of in utero MR (following antenatal US) relative to the updated reference diagnosis at 2-3 years of age (postnatal imaging or post-mortem examination).

Further details of methods and analyses are available in the MERIDIAN protocol [1].

The impact of non-consent to follow-up is anticipated to be very small and will not directly influence the power of the study. All MERIDIAN cases will be retained (using original diagnosis if no consent is received); meaning that the effective sample size is likely to increase where the additional follow-up yields data where previously none was available.

Sample size Project 1

The original MERIDIAN study requires data on 336 children to detect a 10% improvement in diagnostic accuracy. We anticipate the number of participants consenting to repeat examination will be much greater than 336, and the improvement in diagnostic accuracy to be greater still than 10% due to better quality reference data.

Analysis of Project 2

Results from the BSID will allow us to determine the developmental outcome and categorise as; severely impaired, mild-moderately impaired or normal. For the purpose of this analysis, we will consider a severely impaired neuro-developmental outcome as being one where:

- i) The BSID psychomotor component is below 70 (physical impairment)
- ii) The BSID score of <80 on the Cognitive AND language index
- iii) The cognitive and language index has a combined score of <85
- iv) Cerebral palsy on GMFCS
- v) Where there was no BSID assessment, but where the ASQ is <2 SDS below the mean corrected for age

The primary analyses will focus on this as a dichotomous outcome (severe impairment: yes/no). Secondary analyses will further assess whether the prognoses also differentiate children with a BSID of between 70 and 85 (which we tentatively term "mild to moderate impairment") from those with unequivocally normal development (85 or above). We will also assess the actual range of scores within each prognostic category.

There are two primary (and sequential) considerations:

- 1) To quantify the value of prognoses based on MR and on USS
- 2) To assess whether the prognostic value of MR increases relative to that of USS

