Appendix 1 - Developmental assessments

A full assessment will require determination of developmental, sensory, psychomotor and behavioural functioning. We propose to use validated parent completed questionnaires (GMFCS and SDQ) [16-17] where it is not possible to arrange a face to face assessment in order to minimise loss to follow up. These can also be completed via telephone if paper copies are not returned. This is an important and pragmatic approach because it allows us to minimise loss to follow up, whilst robustly determining the true proportion of children with a severe impairment. A face to face assessment will take between 1 and 2 hours and will be completed by a suitably trained paediatrician, physiotherapist or other health professional, and will include:

- BSID III [15] – mental and psychomotor developmental index; time 30-60 minutes.
- Motor function – BSID III and GMFCS [16]; time 5 minutes
- Sensory impairment – parent reported use of hearing or visual aids: time <5 minutes
- Behaviour – SDQ [17] a brief behavioural screening questionnaire which consists of 25 questions

The primary outcomes will be based on BSID III [15], supplemented where necessary by the ASQ [14], and give the proportion of infants surviving without mild, moderate or severe disability at 3 years. This data will be supplemented by using validated questionnaires (GMFCS and SDQ) [16-17] comprising forced-choice items to assess sensory impairment and standardised measures to assess motor and cognitive function and to identify children with:

- Mild/moderate/severe vision or hearing impairment
- Any motor impairment (cerebral palsy with GMFCS level 2)/severe motor impairment (cerebral palsy with GMFCS level 3, 4 or 5)
- Moderate/severe cognitive impairment will also be assessed using ASQ [14] which is a well validated widely used tool appropriate for children at this age, and is easily completed by parents.

Definitions for motor and sensory impairments described above are as defined by British Association of Perinatal Medicine (BAPM 2008).

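### Project 2: a child too impaired for the BSID can be classed severe only through cerebral palsy or a returned ASQ, and the concordance definition, results table and score bands omit both routes

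*Protocol*

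**What the plan says.** All references are to the 2-3 year follow-up protocol.

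- **Section 6, Project 2.** In a small minority of children "a BSID will not be possible, but we will still complete the Gross Motor Function Classification System (GMFCS" or an adapted motor questionnaire, together with the SDQ. The example given is "e.g. spina bifida where children are in a wheelchair". The same pair of instruments is offered when no face-to-face visit can be arranged.
- **Section 7, Analysis of Project 2, limbs (i) to (v).** The GMFCS limb is "Cerebral palsy on GMFCS". The SDQ is in no limb. The ASQ limb is "Where there was no BSID assessment, but where the ASQ is <2 SDS below the mean corrected for age". The primary analyses use this list as a yes/no outcome.
- **Section 2, Project 2.** The definition also admits "evidence of severe disability based on a score <-2SDs for the ASQ, or evidence of cerebral palsy based on GMFCS".
- **Section 5, Project 1.** "The Ages and Stages Questionnaire (ASQ) [15] will also be posted out or given to participants to complete and return with the consent form", with a reminder if forms are not returned. Section 6, Project 1 adds: "The results of this questionnaire will be calculated and recorded".
- **Section 7, concordance paragraph and table.** Severe impairment is restated through BSID scores alone, and the table columns are BSID below 70 and BSID 70 or above.
- **Section 6, Project 2, score bands.** Children are categorised for the CRF by scores of below 70, 70-85 and 85 or more, with no rule for a child who has no score.
- **Appendix 1.** The questionnaire fallback is justified as "robustly determining the true proportion of children with a severe impairment". The same appendix bases the primary outcome on the BSID III, supplemented by the ASQ where needed.

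**The concern.** The instruments named for children who cannot do a BSID are largely not the ones that decide the outcome. The protocol's own example is a wheelchair user with spina bifida, which is not cerebral palsy. The GMFCS can record that child's motor level, but the rule makes no use of it. A physical impairment that would count as severe through a BSID motor score below 70 does not count through the GMFCS unless its cause is cerebral palsy.

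The BSID is missing here because of the severity that the outcome is meant to capture, so the gap is not neutral. These are plausibly children for whom a poor prenatal prognosis was right. If they are left out, true severe cases leave the sensitivity denominator. The retention check in section 7 compares consenting participants with those who refused, so it would not show the loss of a consenting child who could not be assessed.

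**Working it through.** **Step 1. Trace one child.** Take a child with severe motor impairment, no cerebral palsy and no BSID, and apply the limbs in section 7.

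- Limbs (i), (ii) and (iii) need BSID scores, so they cannot be evaluated.
- Limb (iv) needs cerebral palsy, so it is not met.
- Limb (v) is met if an ASQ was returned and is low enough. It is the only open route.

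**Step 2. Compare the places that define the outcome.**

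| Place | BSID | GMFCS | ASQ |
|---|---|---|---|
| Section 2, Project 2 | yes | cerebral palsy | yes, unconditional |
| Section 7, limbs (i)-(v) | yes | cerebral palsy | only if no BSID assessment |
| Section 7, concordance paragraph | yes | no | no |
| Section 7, table | below 70 / 70 or above | no | no |
| Section 6, score bands | below 70 / 70-85 / 85+ | no | no |

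The first two rows give the child a route to the severe class. The last three give none, even with an ASQ in hand. The first two also differ on a partly completed BSID. Section 6 (Risks and Benefits) allows an assessment to be stopped early. Such a child keeps the ASQ route under section 2 but arguably loses it under limb (v). The ASQ cut-off is also worded differently in the two places, and limb (v) read literally points the wrong way.

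**Step 3. Size.** The protocol gives no count of these children and no sensitivity, so the figures here are assumptions except the 50-100 expected non-survivors (section 7, Sample size Project 2), whom the plan counts as poor outcomes. Assume 50 assessable severe survivors, 30 of them rated poor (60%); *k* unassessable children, seven-eighths of them rated poor; and *D* non-survivors, also 60% rated poor.

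Sensitivity with the *k* children left out is (30 + 0.6*D*)/(50 + *D*) = 60%. With them counted as severe it is (30 + 0.6*D* + 0.875*k*)/(50 + *D* + *k*).

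| *D* | *k* = 4 | *k* = 8 | *k* = 12 |
|---|---|---|---|
| 0 | 33.5/54 = 62.0% | 37/58 = 63.8% | 40.5/62 = 65.3% |
| 50 | 63.5/104 = 61.1% | 67/108 = 62.0% | 70.5/112 = 62.9% |
| 100 | 93.5/154 = 60.7% | 97/158 = 61.4% | 100.5/162 = 62.0% |

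With *k* = 8 the shift is 3.8 points if non-survivors are ignored, and 1.4 to 2.0 points once they are counted as planned. Over *k* = 4 to 12 with non-survivors counted, it is 0.7 to 2.9 points. All of this supposes that no ASQ comes back. If half of the 8 are classed severe through the ASQ, the remaining shift is 67/108 - 63.5/104 = 1.0 point (*D* = 50) or 97/158 - 93.5/154 = 0.7 point (*D* = 100).

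**Step 4. The paired comparison and power.** McNemar's test uses only discordant pairs. A child rated poor by both MR and ultrasound is concordant, so losing that child leaves the test unchanged. The planned 90% power with 400 cases cannot be reproduced, because neither the severe/non-severe split nor the discordant proportion is stated. As an illustration, power = Phi((d√n - 1.96√ψ)/√(ψ - d²)), where d = 0.20 is the planned sensitivity gain and ψ the assumed discordant proportion. Losing 5 of an assumed 100 severe cases moves power from 0.965 to 0.957 (ψ = 0.30) or from 0.897 to 0.882 (ψ = 0.40).

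**The case against.** The best defence is the ASQ. It goes to participants with the consent form, is chased by a reminder, is scored and recorded, and is written into limb (v) for children without a BSID. Appendix 1 also names it as the supplement for the primary outcome. On this view the GMFCS and SDQ are extra description, and a child with neither BSID nor ASQ is ordinary missing data. The BSID-only wording later in section 7 can be read as shorthand, since that section also counts non-survivors, who have no BSID, as poor outcomes.

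Much of this stands. A reader might infer that the most impaired children drop out of Project 2 altogether. The documents do not support that, because a low returned ASQ classes them severe under sections 2 and 7. A reader might also infer that unassessed children default to not severe, adding false positives and lowering specificity. No sentence says so.

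Three things remain. The fallback named for these children omits the one instrument that can classify them. Non-survivors have an explicit rule, whereas these children do not have one that is carried through. And the GMFCS limb depends on diagnosis rather than function, so the same impairment is treated differently according to its cause and to which instrument could be used.

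**Conclusion.** The point holds as a gap and inconsistency in the outcome definition. For children in whom a BSID is not possible, the GMFCS/SDQ fallback reaches the severe class only through cerebral palsy, and other such children depend on a returned ASQ. The concordance paragraph, table and score bands contain neither route. Appendix 1's claim of robustness is met for this group only as far as ASQs are returned and the limb (v) wording governs the analysis.

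The effect on sensitivity is probably small: 1.4 to 2.0 points in the case of 8 children with non-survivors counted, and less with ASQ return. This rests on assumed counts and an assumed 60% sensitivity. No effect on the paired MR-ultrasound difference has been shown. The change is still worth making, because the missingness is related to the outcome and the correction is cheap.

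**What to change.** 1. Reconcile section 2, the score bands in section 6, and the limbs, concordance paragraph and table in section 7 into one definition of severe impairment. Carry the ASQ and GMFCS limbs into the primary analysis and its table, and use one wording for the ASQ cut-off.
2. Either let the GMFCS limb apply to functional level whatever the cause, or class a child as severe for the analysis when the assessor records that a BSID was not possible because of the degree of impairment. State how a partial BSID is handled.
3. Record the reason for no or partial BSID (impairment, refusal, distress, missed visit) on the existing developmental assessment CRF.
4. State that a child with no classifying data is missing, not free of severe impairment.

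The cost is protocol wording and one CRF field, with no new assessment or staff. The downside is some assessor judgement, limited by the recorded reason.

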The first consideration is a pre-cursor to the second, since the comparison in 2) is irrelevant if neither MR nor USS contain some measure of useful prognostic information. We will quantify 1) by assessing the concordance between severe neurodevelopmental impairment (BSID score of <80 on the Cognitive AND language index or a combined score of <85 or a motor score of <70) and poor prognosis, based on i) MR and ii) USS. The sensitivity, specificity, positive and negative predictive values of MR and of USS will be reported.

The second consideration is to compare the relative prognostic accuracy of USS and MR. We will do so by calculating the difference in the respective sensitivities and specificities using the paired sample methods recommended by Newcombe [18].

	Outcome	
	Severe impairment (BSID<70) N=xxx	No severe impairment (BSID>=70) N=xxx
USS prognosis		
Poor	n (%)	n (%)
Normal/favourable	n (%)	n (%)
% correctly classified*	$P_{sens (USS)}$	$P_{spec (USS)}$
MR prognosis		
Poor	n (%)	n (%)
Normal/favourable	n (%)	n (%)
% correctly classified*	$P_{sens (MR)}$	$P_{spec (MR)}$
Difference (95% CI)	$P_{sens (MR)} - P_{sens (USS)}$	$P_{spec (MR)} - P_{spec (USS)}$
P-value (McNemar)		

* Here, we consider "Correct" to mean 1) Poor prognosis corresponds to severe impairment, and 2) Normal/favourable prognoses correspond to no severe impairment. The percentages correctly classified reflect 1) sensitivity and 2) specificity respectively.

The secondary outcomes are

- 3) To assess qualitatively the cases for which the USS prognosis and MR prognosis differed, in relation specifically to the original diagnoses
- 4) To look at the concordance in the subgroup of children for which the MR scan was performed within 24 weeks
- 5) To assess ability to predict non-severe impairment

The last of these will further subdivide children without severe impairment (BSID>=70) into "mild-moderate impairment" (BSID between 70 and 85) and "Normal" (BSID>85). The corresponding prognostic categories are "Intermediate" and "Normal or Favourable", and the concordance between the three prognostic categories and the three outcomes will be reported by two-way tabulations.

Sample size Project 2

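### In the Project 2 primary outcome, 'combined score' is undefined and one of the two cognitive-language limbs of severe impairment is idle on each reading examined; on the mean reading, severe also overlaps the protocol's own mild-moderate band

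*Protocol*

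**What the plan says.** All references are to the 2-3 year follow-up protocol.

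- **Section 7, Analysis of Project 2** lists what makes an outcome severe: a motor limb ("The BSID psychomotor component is below 70 (physical impairment"), two cognitive-language limbs ("The BSID score of <80 on the Cognitive AND language index" and "The cognitive and language index has a combined score of <85"), "Cerebral palsy on GMFCS", and an ASQ limb for children without a BSID. It then states: "The primary analyses will focus on this as a dichotomous outcome".
- **How the limbs are joined.** Section 2 (Aims and Objectives, Project 2) joins the BSID limbs with 'or': "defined by BSID score of <80 on the Cognitive AND language index or a combined score of <85 or a motor score of <70". Section 7 repeats this wording where it sets out the sensitivity and specificity analysis.
- **A second definition.** The results table in section 7 heads its column "Severe impairment (BSID<70". Section 6 (Assessments and procedures, Project 2) has the research team code below 70 as severe, 70-85 as mild-moderate and 85 or more as normal. Section 7 also uses 70-85 as the mild-moderate band, both in the secondary analyses and in the last secondary outcome.
- **Scale.** Section 2 pairs a BSID below 85 with an ASQ score between 1 and 2 SDs as non-severe impairment. The norm mean, the SD and the correlation between the indices are not printed, and combined score is not defined anywhere.

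**The concern.** Two limbs joined by 'or' should each be able to decide some case that the other does not. Here the cut-off applied to both indices is lower than the cut-off applied to their combination, so on the mean reading the first limb lies wholly inside the second.

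A redundant limb moves no result by itself. The consequences come from what is left:

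- The outcome depends on a term with no definition. A child scoring 82 on both indices is severe if combined means the mean, and not severe on these limbs if it means the sum.
- On the mean reading the same child is severe under the text rule and mild-moderate under the 70-85 band.
- Severe then means about -1 SD for cognition-language but about -2 SD for motor and ASQ.

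This is the primary yes/no outcome. It decides which children enter the sensitivity denominator and which the specificity denominator when MR and ultrasound prognoses are compared. Changing only the table heading to match the text would leave the idle limb, the undefined term and the overlap with 70-85 in place.

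**Working it through.** **The plan's own figure.** No computed figure is attached to the cut-offs. The nearest is the Project 3 precision statement (about 140 cases, prevalence below 10%, standard error 2.5%): sqrt(0.10 × 0.90 / 140) = 0.0254, which reproduces it.

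**Step 1: is a limb redundant?** Let C and L be the cognitive and language scores. No outside figure is needed for the mean reading.

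- *Mean.* C < 80 and L < 80 give (C + L)/2 < 80 < 85. With integer scores the highest mean is 79. A simulation of 2 million children at each of four correlations (0.4 to 0.7) found none meeting the both-below-80 limb without the combined limb. The converse fails: (82, 82) and (95, 74), with means 82 and 84.5, meet only the combined limb. The first limb is a strict subset of the second.
- *Composite rescaled to mean 100, SD 15.* At (80, 80) the composite is 100 - 40/sqrt(2 + 2r): 71.7 at r = 0, 76.9 at r = 0.5 and 80.0 at r = 1. It is always below 85, so the first limb is again redundant.
- *Raw sum.* C + L < 85 needs an average below 42.5. On a mean-100, SD-15 scale that is (100 - 42.5)/15 = 3.8 SD below the mean on both indices, so the combined limb is practically idle.

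**Step 2: how high is the remaining bar?** Illustration only. Assumed: bivariate normal, mean 100, SD 15 (inferred from the pairing of 85 with 1 SD) and correlation r, which the documents do not give. The mean has SD 15 × sqrt((1 + r)/2), so

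P(mean < 85) = Φ(-1/sqrt((1 + r)/2)) and P(mean < 70) = Φ(-2/sqrt((1 + r)/2)).

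| r | both < 80 | mean < 85 | mean < 70 |
|---|---|---|---|
| 0 | 0.8% | 7.9% | 0.2% |
| 0.5 | 2.8% | 12.4% | 1.05% |
| 0.6 | 3.5% | 13.2% | 1.3% |
| 0.7 | 4.2% | 13.9% | 1.5% |
| 1 (limit) | 9.1% | 15.9% | 2.3% |

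For r = 0.5-0.7 the cognitive-language limbs therefore flag 12.4-13.9% on the mean reading but only 2.8-4.2% on the sum reading, where the both-below-80 limb does the work. The rates also depend on the norm mean: at 105 instead of 100, combined below 85 flags 6.2-7.4%.

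**Step 3: overlap with mild-moderate.** The share of children flagged by mean < 85 whose mean is 70 or more is 1 - P(mean < 70)/P(mean < 85). At r = 0.5 this is 1 - 0.0105/0.1241 = 92%; at r = 0.7 it is 1 - 0.0150/0.1390 = 89%. This takes the 70-85 band to apply to the same mean, since the protocol does not say which BSID score the band refers to.

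**The case against.** The strongest reply has four parts.

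- **Redundancy changes nothing.** On the mean reading, deleting the both-below-80 limb leaves the outcome identical. That is true. What remains is the undefined term, the unequal severity across domains and the overlap with 70-85, and these do change who is classified as severe.
- **It is the conflict with below 70 under another name.** Much of the overlap is that conflict, and if reconciliation settled on below 70 the two limbs would disappear. If the text definition is kept, the limbs need repair in their own right, so both matters should be settled in one edit.
- **The cut-offs were set deliberately.** The amendment log says the scores were updated to match those produced by the BSID III. That shows revision, but the protocol gives no source for 80 and 85 in this arrangement. A reader might infer that the two numbers were exchanged by mistake. The documents do not support this: careless drafting explains a superfluous limb equally well, and the exchanged rule is printed nowhere.
- **The secondary analyses give partial cover.** Section 7 plans to look at the 70-85 band and at the range of scores within each prognostic category. That would show some threshold dependence, but it does not settle the primary outcome.

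A reader might also infer that about one ordinary child in eight is labelled severe. That figure needs a mean, SD and correlation that are not printed, and Project 2 studies fetuses with suspected brain abnormality, not a norm population.

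**Conclusion.** The point holds in this form: combined score is undefined in the Project 2 primary outcome, and on each of the three readings examined (mean, rescaled composite, sum) one cognitive-language limb never, or practically never, decides a case. On the mean reading the cognitive-language part of severe is a combined score below 85, which overlaps the protocol's own mild-moderate band and is about 1 SD less strict than the motor and ASQ limbs.

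The redundancy on the mean reading is algebra. The prevalence figures are illustrations that rest on mean 100 and SD 15: 12.4-13.9% at correlation 0.5-0.7 (7.9-15.9% over correlations 0 to 1), against 1.0-1.5% for a mean below 70 at correlation 0.5-0.7.

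Two stronger readings are not supported. First, severe impairment as a whole does not reduce to combined below 85: motor below 70, cerebral palsy and the ASQ are separate routes, and non-survivors (about 50-100 expected) enter the primary analysis as poor outcomes. Second, the Project 3 prevalence is not shown to be affected. Project 3 takes its categories from Project 2, for which section 6 prints below 70 and section 7 prints the text rule, so the effect depends on which is used. No effect on the size of the MR-ultrasound difference has been calculated either.

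**What to change.** Before any outcome is classified:

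1. Define combined score.
2. Check the 80 and 85 cut-offs against the source of the rule and cite that source.
3. Reconcile section 2, section 6 and section 7 (list, restated definition and table heading) into one definition of severe impairment in which no limb is idle and severe does not overlap mild-moderate. State which BSID score each band refers to.
4. Use that definition for both Project 2 and Project 3.
5. As a sensitivity analysis, report the MR-ultrasound comparison and the prevalence of severe impairment under the two definitions already printed, the text rule and below 70.

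This review does not say which cut-off is right. The cost is protocol wording and one additional table from scores that are collected anyway.
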